5.3 Randomisation and Blinding

Biases and blinding

- Randomisation controls for performance and incorporation biases with respect to the clinical utility of bpMRI in comparison to mpMRI.
- Pathologists will be blinded to MRI type by ensuring the pathology request forms do not provide this information.

Imaging scan data

IP7-PACIFIC	Protocol No: 22CX7488	Imperial College London	V3.0 18 th December 2023

Imaging scans are performed as part of this study. We will also ask for consent from patients to store and use their scan data in future research (academic or commercial) to see if new ways of looking at these scans can detect cancer better in the future. All scans need to be electronically transferred for collation at Imperial in order to facilitate double reporting and therefore will be available for data banking within the Research Data Store (https://www.imperial.ac.uk/admin-services/ict/self-service/research-support/rcs/rds/).

Randomisation process

In randomisation-1, patients with suspected prostate cancer will be allocated in a 1:1 ratio to bpMRI or mpMRI, and those with a suspicious MRI (either bpMRI or mpMRI) who are recommended to undergo targeted biopsy will be allocated 1:1 to image-fusion or visual-registration biopsy (along with non-targeted systematic biopsy as per guidance). Randomisation-2 will be stratified for type of MRI to which participants in the first randomisation are allocated.

	Screening			
Visit	1	2	3	4
Week	0	1-8	1-8	2-12
Informed consent	Х			
Inclusion & exclusion criteria	Х			
Demographics	Х			
Targeted medical history	X ¹			
MRI		Х		
Biopsy (in some patients)			X ²	
Patient questionnaires	X ³	X ³		X ³
Biopsy results				X4
Adverse events			X ⁵	X ⁵

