6. INTERVENTION

6.1 Permanent Discontinuation of Study Intervention and Withdrawal from Study

(i) Permanent discontinuation of study intervention

Subjects may discontinue study intervention for the following reasons:

- At the request of the subject.
- Adverse event/ Serious Adverse Event
- If the investigator considers that a subject's health will be compromised due to adverse events or concomitant illness that develop after entering the study.

(ii) Withdrawal from Study

Withdrawal from the study refers to discontinuation of study intervention and study procedures and can occur for the following reasons:

- Subject decision
- Loss to follow-up

(iii) Procedures for Withdrawal from Study

Patients may decide to opt out of IP7-PACIFIC at any time. This is entirely within their right to do so. Such cases will be reported to the Research Team Office so that no further data are entered onto the database, as specified in the patient information leaflet and appropriate Standard Operating procedure. Data captured before consent was withdrawn will be used in the study, but no further data, beyond this date will be collected or used in any analysis. Reason for withdrawal should be recorded in the eCRF and medical records, if given by the patient. Our sample size calculation assumes a 10% withdrawal rate but if this exceeds that number, we will continue to recruit patients until the target number for each randomisation is met.

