8. STATISTICAL ANALYSES

8.1 Sample Size and power considerations

Randomisation 1: bpMRI vs mpMRI

Consistent with NIHR-HTA PROMIS [[name] et al, 2017], NIHR PRECISION observed a 38% detection of clinically significant prostate cancer (defined as any Gleason >/=3+4 [ISUP Grade Group >/=2]) in patients with suspected prostate cancer having pre-biopsy mpMRI compared to 26% having a traditional biopsy alone without pre-biopsy MRI [Kasivisvanathan et al, 2018]. To preserve at least 50% of the improvement in detection rates implies exclusion of a 6% absolute reduction from a 38% detection rate in order to recommend a switch from mpMRI to bpMRI. We have chosen a non-inferiority margin of 5% which strikes a balance between our clinician survey, the patient perspective, ensuring improvement on the previous standard of care and an achievable sample size. To provide 90% power to confirm non-inferiority and exclude an absolute 5% reduction in detection rate of clinically significant prostate cancer from an estimated 38% in both arms, using an overall 0.05 significance level for a one-sided test, requires 3230 men (1615/arm). A target sample size of 3600, would therefore account for an assumed attrition rate of about 10%.

IP7-PACIFIC Protocol No: 22CX7488	Imperial College London	V3.0 18 th December 2023
-----------------------------------	-------------------------	-------------------------------------

The expected detection rates of clinically significant prostate cancer (defined as any Gleason >/=3+4 [ISUP Grade Group >/=2])are 55% (visual-registration) and 65% (image-fusion). Our clinician and patient groups indicated that >/=10% improved detection rate using image-fusion is acceptable for adoption. In PRECISION and PROMIS, approximately 70-75% were recommended for biopsy following mpMRI. Assuming 70% will be recommended for biopsy and conservatively assuming a further 10% attrition, we anticipate at least 2000 patients from randomisation-1 would be eligible for randomisation-2. This provides ample power (>95%) to detect the absolute 10% difference described above using a two-sided test at the 5% significance level. Include the number of subjects to be enrolled, reason for choice of the sample size, including details of the sample size estimation and the power of the study and clinical justification.

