For each randomisation, the number and proportion of clinically significant cancers detected in the randomised population will be reported by trial arm. Group differences will be quantified by the risk difference with two-sided confidence intervals at a level appropriate to the significance level pre-specified in the sample size. Detection rates will be compared by trial arm using mixed models with adjustment for trial arm allocation of co-enrolled trial and random effect by centre. The treatment effect coefficients will be presented with confidence intervals and associated p-value. The primary analysis will be conducted on an intention-totreat (ITT) basis, where patients with missing outcomes are assumed not to have clinically significant prostate cancer. A modified ITT analysis will be performed excluding patients who did not complete the diagnostic tests, and for the non-inferiority comparison a per protocol analysis including only those undergoing randomly assigned interventions. A pre-specified statistical analysis plan will be drafted detailing intended analyses for primary and secondary outcomes. It will be approved by the IDMC and agreed prior to analysis.

Cost-effectiveness analysis

A within trial cost-effectiveness analyses will estimate the incremental cost per true positive detected and incremental cost per correct diagnosis. Estimates of diagnostic performance will be based on the trial analysis and costs will be estimated from the NHS and PSS perspective using a micro-costing approach for tests. Deterministic (to explore plausible alternatives e.g., quantity of resources used or unit costs) will be combined with stochastic

IP7-PACIFIC Protocol No: 22CX7488	Imperial College London	V3.0 18 th December 2023
-----------------------------------	-------------------------	-------------------------------------

sensitivity analysis (used to explore statistical imprecision in estimates of costs, effects and cost-effectiveness).

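### Randomisation 1: the primary ITT rule counts missing outcomes as no significant cancer, while the sample size treats the same 10% as lost; with balanced, uninformative missingness the 5% error becomes about 9.3%

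*Protocol*

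**What the plan says.** Protocol section 8.3 (main study clinical outcomes analysis) sets one rule for both randomisations. The primary analysis is ITT, "where patients with missing outcomes are assumed not to have clinically significant prostate cancer". A modified ITT analysis that leaves out patients with incomplete diagnostic tests is also planned and, for the non-inferiority comparison, a per protocol analysis. Neither is called primary, and the section does not say that they must agree with ITT before non-inferiority is concluded.

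Protocol section 8.1 sizes randomisation 1. Its aim is "To provide 90% power to confirm non-inferiority" and to "exclude an absolute 5% reduction in detection rate of clinically significant prostate cancer from an estimated 38% in both arms", at a one-sided 0.05 level. This gives 3230 men, 1615 per arm. It continues: "A target sample size of 3600, would therefore account for an assumed attrition rate of about 10" per cent. Section 6.1 repeats the figure: "Our sample size calculation assumes a 10% withdrawal rate". It adds that recruitment will go on if withdrawals exceed this, and that no data are collected after withdrawal.

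**The concern.** Section 8.1 takes the 10% out of the analysis: 3230 patients with outcomes are needed, so 3600 are recruited. Section 8.3 puts them back in the denominator as non-events. Adding the same share of non-events to both arms multiplies the difference between arms by one minus that share. This is cautious for a superiority test such as randomisation 2. For a non-inferiority test against a fixed absolute margin it works the other way, because a real deficit looks smaller.

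At stake is the error rate of the trial's main claim, that bpMRI can replace mpMRI. Recruiting further when withdrawals exceed 10% does not help, because the dilution depends on the proportion missing and not on the number recruited.

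Patients not biopsied after a non-suspicious MRI are a separate matter. They completed the pathway and are true non-detections.

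**Working it through.** **Inputs.** Section 8.1: 38% in both arms under the alternative, hence 38% vs 33% at the margin; margin 0.05; one-sided alpha 0.05 (z = 1.645); power 90% (z = 1.282); 10% attrition; 3600 randomised. Section 5.3: 1:1 allocation, so 1800 per arm. Assumptions not in the protocol: the pattern of missingness, varied below, and an unadjusted risk difference in place of the mixed model.

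**The plan's own figure.** n per arm = (1.645 + 1.282)² × 2 × 0.38 × 0.62 / 0.05² = 1614.1, rounded up to 1615, so 3230 in total. Then 3230 / 0.9 = 3589, consistent with 3600. The stated size reproduces, and it does so by treating the 10% as absent from the analysis.

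**Error under the section 8.3 rule.** With a proportion d missing, the analysed rate is p(1 − d). Writing c and t for the analysed mpMRI and bpMRI rates:

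- SE = √{[c(1 − c) + t(1 − t)] / 1800}
- P(declare non-inferiority) = Φ((0.05 − (c − t)) / SE − 1.645)

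At 10% missing in each arm and unrelated to outcome:

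- c = 0.38 × 0.9 = 0.342; t = 0.33 × 0.9 = 0.297; difference 0.045
- SE = √[(0.342 × 0.658 + 0.297 × 0.703) / 1800] = 0.01552
- Φ(0.005 / 0.01552 − 1.645) = 9.3%

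A simulation of 1,000,000 trials also gives 9.3%. Put the other way, a measured 5-point loss corresponds to 5 / 0.9 = 5.6 points among patients with outcomes.

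| Missing, mpMRI / bpMRI | One-sided error at 38% vs 33% |
|---|---|
| 0% / 0% | 5.0% |
| 2.5% / 2.5% | 5.9% |
| 5% / 5% | 6.9% |
| 10% / 10% | 9.3% |
| 15% / 15% | 12.4% |
| 20% / 20% | 16.4% |
| 8% / 12% | 1.3% |
| 9% / 11% | 3.8% |
| 11% / 9% | 19.3% |
| 12% / 8% | 34.2% |

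**Missingness related to outcome.** Let 38% vs 33% be the rates had every randomised patient been tested, with 10% missing per arm. If the missing patients would have had half the detection rate of the others, the error is 7.0%. If they would have had none, it is 5.0%.

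**Patients with outcomes only.** With 1620 per arm (1800 × 0.9), the error is 5.0% (simulated 5.01%). Power at 38% in both arms is Φ(0.05 / √(2 × 0.38 × 0.62 / 1620) − 1.645) = 90.1%. This recovers the design in section 8.1.

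**Power under the diluted ITT.** Φ(0.05 / √(2 × 0.342 × 0.658 / 1800) − 1.645) = 93.5%. Keeping the rule but scaling the margin to 0.9 × 5 = 4.5 points gives 5.0% error and Φ(0.045 / 0.01581 − 1.645) = 88.5% power.

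**The case against.** The strongest reply is that the endpoint in section 2.3 is cancer detected on biopsy over everyone randomised. On that scale a patient who never completes testing is a non-detection by definition, the 4.5-point difference is the true one, and the test has its stated 5% error. Section 8.1 never says that the 38% and the margin are for patients with outcomes; that is inferred from the inflation to 3600. This stands. It means the 9.3% is conditional, but it leaves the two sections handling the same 10% differently.

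Second, the margin has some slack. Section 8.1 derives a 6-point limit (half of mpMRI's gain) and then chooses 5. At 38% vs 32% with 10% missing per arm, the chance of declaring non-inferiority is Φ((0.05 − 0.054) / 0.01546 − 1.645) = 2.8%. It reaches 5% only when 6(1 − d) = 5, that is at 16.7% missing. This lowers the gravity of the point but does not restore 5% error at the margin actually chosen. The pilot table in section 8.3 also rates 80% outcome completeness as green; if 20% stayed missing, a measured 5-point loss would be 5 / 0.8 = 6.25 points among patients with outcomes, beyond the 6-point limit.

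Third, biopsy results come from routine clinical records, so real loss may be well below 10%; at 2.5% the error is 5.9%. This is fair.

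Fourth, the undiluted analyses are already planned, and agreement rules and imputation are commonly left to the SAP. Their absence from the protocol is not the fault here. The fault is that the protocol itself fixes ITT with this rule as primary, on a scale that its sample size does not use.

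A reader might infer that the trial's true error is simply 9%, or that poorer follow-up always favours bpMRI. The documents support neither. Heavier loss under bpMRI makes the rule conservative, and the protocol gives no attrition by arm.

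**Conclusion.** The inconsistency between sections 8.1 and 8.3 is real and touches the primary claim of randomisation 1. If missingness is equal by arm and unrelated to outcome, and the margin is meant for patients with outcomes, the one-sided error at 10% attrition is about 9.3% instead of 5%. The size depends on those conditions: small imbalances move it to 3.8% or 19.3%, and on an all-randomised margin the nominal 5% holds. Error control that rests on an unknown missingness pattern and an unstated scale is not what section 8.1 promises. The planned supporting analyses would expose the problem but, as written, do not prevent a claim resting on the diluted result alone.

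A reader might also conclude that ITT should give way to an analysis of completers as the sole basis for the decision. That does not follow. Completion may depend on arm, since only mpMRI uses contrast and section 7.4 lists abandoned scans and contrast reactions among expected events. A completers-only decision would abandon the randomised comparison.

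**What to change.** In section 8.3, for randomisation 1:

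- Keep the ITT analysis, but claim non-inferiority only if the modified ITT and per protocol analyses also exclude the 5-point loss. The modified ITT should preferably use multiple imputation of missing outcomes from baseline data and MRI score.
- Define missing, and state that patients not biopsied after a non-suspicious MRI are non-detections and not missing.
- Add a tipping-point analysis that varies the missing outcomes separately by arm.

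In section 8.1, state whether the 38% and the 5-point margin refer to all randomised patients or to patients with outcomes.

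Leave the rule unchanged for randomisation 2, where it is conservative under balanced loss.

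The cost is wording in the protocol, matched in the SAP and settled before unblinded analysis. Power falls from about 93.5% under the diluted ITT to about the 90% already stated, or slightly less because all three analyses must succeed. No change in recruitment is needed to keep roughly the stated power.

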Unit costs of these resources will come from study centres and routine data sources (e.g. salary scales, etc). These unit costs will be combined with resource use to estimate the cost for each trial participant. Regression techniques will be applied to data on total costs to determine any difference between the two testing strategies. We will assume effects (clinically significant cancers detected) are the same when the estimates of effects (including the extremes of a confidence interval) rule out a minimally important question. In this case, we will present the results as a cost-minimisation analysis. However, if the confidence intervals do not rule out a minimally important difference, we will conduct a formal cost-effectiveness analysis. This will incorporate a stochastic analysis to explore statistical imprecision in the estimates of costs, effects and cost effectiveness. The results of this will be presented as cost and effect plots and cost-effectiveness acceptability curves. Further deterministic sensitivity analysis will be conducted to explore plausible alternatives e.g. around the quantity of resources used or unit costs.

Model based analysis

The model based analysis will be required to explore the impact of two different features: (i) changes in the number of patients who can be imaged as a result of possible reductions in imaging time; (ii) estimation of long-term impacts should clinically important differences not be ruled out. For (i) the focus will be on prostate cancer patients as these could also be considered as a proxy for other patients that could benefit for imaging.

For (ii) the results of the within trial economic evaluation if presented as an incremental cost effectiveness ratio will be difficult to interpret as there is no readily accepted threshold values for society's willingness to pay per additional clinically significant cancer detected. Therefore, we will conduct a model-based cost-utility analysis.

For a model addressing both (i) and (ii) the results will be reported as incremental cost per QALY gained (but see section on resource impact below). Both costs and QALYs will estimated over the estimated patient lifetime. As outcomes for individuals modelled will occur beyond a 12-month period both health benefits and costs will be discounted using the current recommended rate of 3.5% for both costs and benefits at the base case [NICE Guideline, 2013].

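### The within-trial economic analysis sets detection equal, and reports costs only, once an important difference is ruled out; this conflicts with the unconditional economic endpoints

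*Protocol*

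**What the plan says.** The rule stands in Protocol section 8.3, Within trial analysis. It applies when the estimate of effect, including the extremes of its confidence interval, excludes a minimally important difference. (The word printed there is *question*; *difference* is plainly meant, since the next branch uses it.) The protocol then says: "We will assume effects (clinically significant cancers detected) are the same". It continues: "In this case, we will present the results as a cost-minimisation analysis". The formal cost-effectiveness analysis, with its stochastic analysis, cost and effect plots and acceptability curves, is described only for the other branch. Neither a size for the important difference nor a confidence level is given.

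The Model based analysis part gives the model two purposes. The first is the effect of imaging more patients. The second carries a similar condition: "ii) estimation of long-term impacts should clinically important differences not be ruled out".

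Other places attach no condition. Sections 2.2 and 2.4 list incremental cost per clinically significant cancer detected and per correct diagnosis. In section 8.3, both Cost-effectiveness analysis and the opening of Within trial analysis say that incremental cost per true positive and per correct diagnosis will be estimated. Cost-effectiveness analysis also plans stochastic sensitivity analysis and a cost-utility model reporting cost per QALY.

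**The concern.** Excluding a loss of a given size does not show that the loss is zero. The rule replaces an estimate and its uncertainty by exactly zero, and with them drops the joint uncertainty of cost and effect. The economic question for a shorter scan without contrast is whether any saving is worth any loss of detection. The rule takes that trade out of the within-trial result after a successful non-inferiority finding, which is when adoption would be considered. It also leaves a listed endpoint without a value: if detection is set equal, incremental cost per significant cancer detected has a denominator of zero.

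**Working it through.** **Inputs, all from Protocol section 8.1 unless stated.** Margin: "We have chosen a non-inferiority margin of 5" percentage points. Detection rate: 38%, "from an estimated 38% in both arms". Error rate: "using an overall 0.05 significance level for a one-sided test". Power: 90%. Size: "requires 3230 men (1615/arm"), with a target of 3600, or 1800 per arm at the 1:1 allocation of section 5.3. Section 8.3 (Main study clinical outcomes analysis) asks for two-sided intervals at a level matching the sample-size significance level. For a one-sided 0.05 test that is 90%. Because the economic rule names no level, 95% is shown as well.

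**Assumption.** The important difference is the 5-point margin, the only figure that the protocol attaches to detection in this comparison.

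**Step 1: the plan's own figure.** n per arm = (1.645 + 1.282)² × 2 × 0.38 × 0.62 / 0.05². This gives 1615 per arm, 3230 in all, which agrees with the protocol.

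**Step 2: the largest observed loss still set to zero.** SE = √(2 × 0.38 × 0.62 / n), and largest loss = 5 − z × SE, in percentage points.

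| n per arm | SE | 90% half-width | Largest loss, 90% | 95% half-width | Largest loss, 95% |
|---|---|---|---|---|---|
| 1615 | 1.71 | 2.81 | 2.19 | 3.35 | 1.65 |
| 1800 | 1.62 | 2.66 | 2.34 | 3.17 | 1.83 |

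The range is about 1.7 to 2.3 per 100 men. Against a 38% rate, 2.19 points is 2.19/38, or about 6% of the significant cancers detected. With control rates from 30% to 45% and the same two sizes, the limit is 2.1 to 2.5 points (90% interval) or 1.6 to 2.0 (95% interval).

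**Step 3: what the interval would look like at the limit.** At 1615 per arm with a 90% interval it runs from a loss of 5 points to a gain of 2.81 − 2.19 = 0.62 points. The data would be compatible with no loss, and equally with a loss just under 5 per 100.

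**Step 4: how often a real loss would trigger the rule.** If the true loss were 2 points, the interval would exclude 5 points in about 55% of trials at 1615 per arm with a 90% interval, or 42% with a 95% interval. At 1800 per arm the figures are 59% and 46%.

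**Step 5: the passages side by side.**

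| Item | Without condition | With condition |
|---|---|---|
| Cost per significant cancer or true positive, and per correct diagnosis | 2.2; 2.4; 8.3 Cost-effectiveness analysis; opening of 8.3 Within trial analysis | Rule in 8.3 Within trial analysis |
| Stochastic analysis of cost and effect | 8.3 Cost-effectiveness analysis | Same rule: only if the difference is not ruled out |
| Model of long-term effect | 2.2; 2.4; 8.3 Cost-effectiveness analysis | 8.3 Model based analysis, second purpose; 8.3 Justification, where the cost-utility analysis mitigates an inconclusive result |

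With detection set equal, cost per significant cancer (or true positive) cannot be computed. Cost per correct diagnosis is not blocked arithmetically, but a cost-minimisation presentation has no place for it.

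**The case against.** Several stronger readings are tempting, and the protocol does not support them.

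- *The whole economic evaluation would report costs only.* The rule governs the within-trial analysis. Section 8.3 still plans a cost-per-QALY model using the tests' sensitivity and specificity from the trial, with probabilistic sensitivity analysis and acceptability curves. What remains is ambiguity: the long-term purpose is worded conditionally, and the model's short-term part is expected to mirror the within-trial analysis. A reader cannot tell whether the estimate or zero enters the model after a non-inferior result. That zero is used throughout is not established.
- *A loss would be hidden.* It would not. The clinical analysis reports proportions by arm and the risk difference with its interval.
- *A cost-only comparison must favour bpMRI.* Section 1 gives scan tariffs of £239 and £141, but section 8.3 compares total cost per participant, with micro-costed tests and other care to the end of follow-up. It says only that bpMRI may be less costly. For the same reason, dividing the tariff gap by the loss does not give the saving per missed cancer that the planned analysis would yield.
- *The limit is the expected loss.* It is the largest observed loss that still passes, and step 3 shows an interval there that includes no loss.

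It can also be said that cost-minimisation after a prespecified exclusion is a declared choice. That is fair as far as it goes. But the choice gives no threshold and contradicts endpoints that the same document declares without condition.

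**Conclusion.** The concern holds for the within-trial economic analysis. A stated rule sets the effect to zero after a non-inferior result and conflicts with sections 2.2 and 2.4 and other parts of 8.3. If the important difference is 5 points and detection is 38%, an observed loss of up to about 1.7 to 2.3 significant cancers per 100 men would be treated as none in that analysis. The range covers 1615 to 1800 per arm and 95% or 90% intervals, and ignores any effect of centre or covariate adjustment on the standard error. A different important difference would move the limit, and the protocol does not give one. The primary clinical conclusion is not affected.

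**What to change.** In Protocol section 8.3, Within trial analysis:

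- Always estimate incremental cost and incremental detection jointly, with the cost-effectiveness plane and acceptability curve, whatever the non-inferiority result.
- Keep cost-minimisation only as a secondary scenario. If it stays, state the size of the important difference and the confidence level that define it, and correct the misprinted word.
- State in Model based analysis that the estimated effect and its uncertainty always enter the model.
- Reconcile these parts with sections 2.2 and 2.4 and with Cost-effectiveness analysis and Justification for an economic evaluation in 8.3.

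The cost is a wording change and a little more analysis and reporting. No new data are needed, and the sample size does not change.
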